***Cohort 3 (Patients with melanoma who have previously been treated and progressed on a PD-1 or PD-L1-blocking antibody)***

A maximum of 52 patients will be enrolled in cohort 3. A true ORR of 25% is hypothesized. An ORR greater than 10% is considered the lower threshold for antitumor activity that would warrant continued development in this setting. Based on the design elements specified above, the single proportion (or one sample) binomial test will be used. Ninety-six percent 1-sided confidence interval of the observed one sample proportion will be calculated. The trial will be considered a success if the lower limit of 96% confidence interval is greater than 10%.

Syndax will conduct one administrative analysis when at least 60% (31 out of 52 patients) of patient information have accrued in cohorts 3 for decision making for late phase development planning. This administrative look will not lead to stopping of the study. Nonetheless, 0.01 alpha is being allocated to spend for the first administrative look and leaving 0.04 alpha for the final analysis.

***Cohort 4 (Patients with CRC who have not previously been treated on a PD-1 or PD-L1-blocking antibody)***

A maximum of 84 patients will be enrolled in Cohort 4. A true ORR of 15% is hypothesized. An ORR greater than 5% is considered the lower threshold for antitumor activity that would warrant continued development in this setting. Based on the design elements specified above, up to 37 patients may be enrolled during the first stage: if less than or equal to 2 patients achieve a CR or PR, confirmed or unconfirmed, then enrollment will terminate; otherwise, 47 additional patients will be enrolled during the second stage. Upon completion of the second stage, if 8 or more patients out of the 84 enrolled achieve CR or PR, then the true ORR for the combination regimen likely exceeds 5%, the lower threshold of acceptable antitumor activity. Alternatively, if 7 or fewer patients achieve an objective response at the end of the second stage, then the true ORR is likely 5% or lower and further evaluation of the combination

therapy may not be pursued in this setting. If the true ORR is 5% or less, then the expected sample size is 50.2, with probability of terminating enrollment at the end of the first stage equal to 72%.

## **12.2 Populations for Analysis**

The Full Analysis Set (FAS) will serve as the primary population for the analysis of tumor response and other efficacy-related data. The FAS is a subset of all enrolled patients, with patients excluded for the following reasons:

- Failure to receive at least one dose of entinostat and pembrolizumab
- Lack of baseline data for those analyses that require baseline data

A supportive analysis using the Per-Protocol (PP) set may be performed by excluding patients with important deviations from the protocol that may substantially affect the results of the primary efficacy analyses. The final determination on protocol violations, and thereby the composition of the PP set, will be made prior to locking the clinical database and final analysis and will be documented in a separate memo.

The safety population will be used for the analysis of safety data in this study. The safety population will consist of all patients who receive at least one dose of entinostat and pembrolizumab. At least one laboratory or other safety-related assessment subsequent to at least one dose of entinostat and pembrolizumab is required for inclusion in the analysis of a specific safety parameter. To assess change from baseline, a baseline measurement is also required.

A patient that experiences an adverse event meeting DLT criteria during C1 or who receives the full dose of pembrolizumab and all doses of entinostat during C1 without experiencing a DLT, is considered a DLT-evaluable patient.

## **12.3 Analysis Schedule**

### **12.3.1 Safety Monitoring**

The safety and tolerability of the investigational treatments will be monitored throughout the course of the study by the Investigators and Sponsor Study Physician(s) including ongoing review of serious adverse events and other safety trends. Frequent meetings will be held during Phase 1 to review safety aspects of the study and to render dose escalation decisions as applicable.

Safety and tolerability data that will be reviewed by the Sponsor Study Physician(s) will include, but are not limited to: adverse events, laboratory test results, and patient discontinuations. Note that all serious

adverse events must be reported to the Sponsor within 24 hours of discovery or notification of the event. No formal safety stopping rules are specified in the protocol. However, if any significant safety issues arise, a decision to modify or terminate the trial will be made by the Sponsor in collaboration with the study's Steering Committee.

### **12.3.2 Efficacy Monitoring**

An interim analysis of ORR will be performed for each tumor type after enrollment in the first stage is complete in the Expansion Phase. Patients will be followed for response for a minimum of two cycles following the initiation of study drug. Patients who die or discontinue treatment during the first two cycles because of radiographic and/or clinical evidence of disease progression will be considered nonresponders. Enrollment in the second stage will be initiated once enrollment in the first stage is complete and the minimum number of responders is observed, as described in [Section 12.1.2](#). If the minimum is observed prior to the completion of enrollment, then the transition between the first and second stages will occur without interruption. If the minimum is not observed at the time enrollment is completed, then enrollment in the second stage will be held until the continuation criterion is met.

### **12.4 Statistical Methods**

The safety and efficacy analyses will be presented by study phase. For the escalation phase, tabulations will be provided by dose cohort and overall. For the Expansion Phase, tabulations will be provided by tumor type and overall. Some analyses may be performed based on the dose escalation and Expansion Phases combined.

The statistical analyses for this study will be performed using SAS® version 9.2 or later (SAS Institute, Inc., Cary, NC). Programming specifications will be prepared which describe the datasets and variables created for this study. The datasets will be prepared using the most recent version of CDISC's Study Data Tabulation Model (SDTM) and Analysis Dataset Model (ADaM). The source SDTM and ADaM datasets from which a statistical analysis is performed (including interim safety and efficacy reviews) will be archived with the Sponsor.

### **12.4.1 Disposition of Patients**

The number of patients included in the efficacy and safety analyses will be summarized, along with the reason for exclusion from one or more analysis populations. Patients discontinuing from study drug and

the primary reason for discontinuation will be summarized. Patients withdrawing from study and the primary reason for withdrawal will be summarized in a similar manner.

#### **12.4.2 Demographics and Baseline Characteristics**

Descriptive summaries of demographic and baseline characteristics will be tabulated by study phase and overall. For the Dose Escalation/Confirmation Phase, tabulations will be provided by dose cohort and overall. For the Expansion Phase, tabulations will be provided by tumor type and overall.

#### **12.4.3 Extent of Exposure**

The overall duration of study drug administration (in months) and the total number of cycles initiated will be tabulated for each patient and summarized by study phase. For the escalation phase, tabulations will be provided by dose cohort and overall. For the Expansion Phase, tabulations will be provided by tumor type and overall. For patients who receive entinostat, the average dose of entinostat (in mg) administered and cumulative dose (in mg) administered will be calculated. These data will be further summarized by calculating the mean, standard deviation, median, and range of these values. The number and proportion of patients with one or more dosage modification of study drug will be tabulated by treatment arm along with the reason for dosage modification. The primary reason for study drug discontinuation will be tabulated in a similar manner.

Similar tabulations will be provided for the administration of pembrolizumab.

#### **12.4.4 Concomitant Medications**

Prior and concomitant medications will be coded to generic term using the current version of the World Health Organization Drug Dictionary and will be tabulated and listed by patient.

#### **12.4.5 Efficacy Analysis**

Efficacy analyses will be conducted using the Full Analysis Set and, where appropriate, the Per-protocol Set.

ORR will be estimated for each cohort evaluated in the Expansion Phase using irRECIST, as the primary endpoint. Crude proportion of patients with best overall response of CR or PR, along with a 2-sided 95% CI, will be calculated for cohorts 1 and 4. The width of the CI will be adjusted to account for the multistage design (Atkinson 1985). Additionally, a 90% one-sided CI of the form  $(\pi_L, 1]$  will be reported since the sample size for the Expansion Phases for cohorts 1 and 4 were determined using a one-sided

significance level of 10%. Crude proportion of patients with best overall response of CR or PR, along with a 2-sided 98% CI, will be calculated for cohorts 2 and 3. CBR at 6 months will be analyzed in a similar manner.

DOOR will be calculated for patients who achieve a CR or PR and is defined as the number of months from the start date of the response (and subsequently confirmed) to the first date that recurrent disease or PD is documented. PFS is defined as the number of months from the date of the first dose of study drug to the earliest of documented PD or death due to any cause without prior progression. OS is defined as the number of months from the first dose of study drug to the date of death due to any cause. DOOR, PFS, and OS will be summarized descriptively using the Kaplan-Meier method with 95% confidence intervals (CIs) calculated using Greenwood's formula. Median follow-up for each endpoint will be estimated according to the Kaplan-Meier estimate of potential follow-up. PFS rate at 6 months and corresponding 95% CIs will be estimated using the Kaplan-Meier method. Greenwood's formula will be used to calculate the standard errors of the Kaplan-Meier estimate and upper and lower limits of the 95% CI.

An analysis of efficacy endpoints also will be performed, with response determined using RECIST, version 1.1.

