#### 12.1.2 Expansion Phase

In the Expansion Phase of the study, the safety and preliminary antitumor activity of entinostat when administered at the RP2D with pembrolizumab will be explored in up to 4 cohorts of adult solid tumors as previously defined. Up to 252 patients are planned to be enrolled among the 4 cohorts. Patients will be enrolled in each cohort according to a single-arm study design with ORR, as determined by irRECIST, as the primary endpoint. The Expansion Phase will be carried out in 2 stages so that enrollment for 1 or more of the cohorts evaluated can terminate early in the event the antitumor activity of the combination regimen is not sufficient. The decision to terminate or continue enrollment for each cohort will be made independently of the other. The number of patients evaluated in each stage and the minimum number of responders needed to continue to the next stage, as described for cohort 1, was determined based on the optimum version of Simon's 2-stage design ([Simon 1989](#)), with 80% power and 1-sided significance level of 10%. For cohort 4, the number of patients evaluated in each stage and the minimum number of responders needed to continue to the next stage was determined based on the optimum version of Simon's

2-stage design, with 90% power and 1-sided significance level of 5%. For cohorts 2 and 3, the number of responders needed to declare the study a success was based on single proportion binomial test with 90% power and 1-sided significance level of 5%. Note that the protocol may be amended to allow for enrollment of additional or different cohorts, for example, patients with PD-L1-positive NSCLC, based on emerging data during study conduct.

Syndax will conduct one administrative analysis when at least 60% (42 out of 70 patients in cohort 2, 31 out of 52 patients in cohort 3) of patient information have accrued in cohorts 2 and 3 for decision making for late phase development planning. This administrative look will not lead to stopping of the study. Nonetheless, 0.01 alpha is being allocated to spend for the first administrative look and leaving 0.04 alpha for the final analysis.

***Cohort 1 (NSCLC patients with squamous cell and adenocarcinoma histology who have not been previously treated with a PD-1 or PD-L1-blocking antibody)***

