A maximum of 46 patients will be enrolled in Cohort 1. A true ORR of 35% is hypothesized for both tumor types. An ORR greater than 20% is considered a lower threshold for antitumor activity that would warrant continued development. Based on the design elements specified above, up to 13 patients may be enrolled for either tumor type during the first stage: if 2 or fewer patients achieve an objective response (CR or PR), confirmed or unconfirmed, then enrollment will terminate; otherwise, 33 additional patients will be enrolled during the second stage. Upon completion of the second stage, if 13 or more patients out of the 46 enrolled achieve CR or PR, then the true ORR for the combination therapy likely exceeds 20%, the lower threshold of acceptable antitumor activity. Alternatively, if 12 or fewer patients achieve an objective response at the end of the second stage, then the true ORR is likely 20% or lower and further evaluation of the combination therapy may not be pursued for that tumor type. If the true ORR is 20% or less for a tumor type, then the expected sample size is 29.4, with probability of terminating enrollment at the end of the first stage equal to 50%.

***Cohort 2 (Patients with NSCLC (any histology) who have previously been treated and progressed on a PD-1 or PD-L1-blocking antibody)***

A maximum of 70 patients will be enrolled in Cohort 2. A true ORR of 15% is hypothesized. A response rate greater than 5% is considered the lower threshold for antitumor activity that would warrant continued development in this setting. Based on the design elements specified above, the single proportion (or one sample) binomial test will be used. Ninety-six percent 1-sided confidence interval of the observed one

sample proportion will be calculated. The trial will be considered a success if the lower limit of 96% confidence interval is greater than 5%.

Syndax will conduct one administrative analysis when at least 60% (42 out of 70 patients) of patient information have accrued in cohorts 2 for decision making for late phase development planning. This administrative look will not lead to stopping of the study. Nonetheless, 0.01 alpha is being allocated to spend for the first administrative look and leaving 0.04 alpha for the final analysis.

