3.8 Efficacy Analysis

Efficacy analyses will be performed using the FAS and, where appropriate, the Per-Protocol Set. ORR will be estimated for each cohort evaluated in the Expansion Phase using irRECIST as the primary endpoint. Crude proportion of patients with best overall response of CR or PR, along with a 2-sided 95% CI, will be calculated for each cohort. The width of the CI will be adjusted to account for the multistage design (Atkinson, 1985). Additionally, a 90% one-sided CI of the form $(\pi, 1]$ will be reported for cohort 1 and a 95% one-sided CI will be reported for cohort 4 since the sample size for the Expansion Phases for cohorts 1 and 4 were determined using a one-sided significance level of 10%, 5%, respectively.

Crude proportion of patients with best overall response of CR or PR, along with a 2-sided 92% CI will be calculated for cohorts 2 and 3. ORR based on RECIST 1.1 will be analyzed in a similar manner.

Clinical Benefit Rate

Clinical benefit rate, as determined by irRECIST, will be estimated based on the crude proportion of patients in each cohort whose best overall response during the course of study treatment is a irCR, irPR, or irSD lasting for at least 6 months. Stable disease based on irRECIST will be measured from the start date of study treatment until the criteria for irPD is first met. Approximate 2-sided 95% CIs will be calculated for each cohort. Clinical benefit rate, as determined by RECIST 1.1, will be estimated based on the crude proportion of patients in each cohort whose best response during the course of study treatment is a CR, PR, or SD lasting for at least 6 months. Stable disease based on RECIST 1.1 will be measured from the start date of study treatment until the criteria for PD is first met. Approximate 2-sided 95% CIs will be calculated for each cohort.

Progression-free Survival

The PFS, defined as the number of months from first dose date to PD or death due to any cause, whichever occurs first. Disease assessments will continue until PD, even

after the originally assigned study treatment is discontinued. For purposes of analysis, 1 month is considered 30.4375 days. The duration of PFS as determined by RECIST 1.1 (Eisenhauer 2009) and irRECIST (Seymour 2017) will be summarized descriptively using the Kaplan-Meier method (Kaplan 1958). The PFS at 6 months by irRECIST and RECIST 1.1 will be analyzed in a similar manner.

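### Protocol 12.4.5 gives Cohorts 2, 3 and 4 confidence levels for the primary ORR that do not match their design alpha; the SAP changes them without recording the departure

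*Protocol*

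**What the plan says.** **Design, Cohorts 2 and 3.** Protocol 12.1.2 bases these cohorts on a "single proportion binomial test with 90% power and 1-sided significance level of 5" per cent. Because of an administrative look, "0.01 alpha is being allocated to spend for the first administrative look and leaving 0.04 alpha for the final analysis". For each cohort, "Ninety-six percent 1-sided confidence interval of the observed one sample proportion will be calculated". For Cohort 2, "The trial will be considered a success if the lower limit of 96% confidence interval is greater than 5" per cent; for Cohort 3, "The trial will be considered a success if the lower limit of 96% confidence interval is greater than 10" per cent. SAP 2.3.1 repeats these rules and equates 96% one-sided with 92% two-sided.

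**Reporting in the Protocol.** Section 12.4.5 gives the crude ORR "along with a 2-sided 98% CI, will be calculated for cohorts 2 and 3". For Cohorts 1 and 4 it gives a multistage-adjusted two-sided 95% interval, then continues: "Additionally, a 90% one-sided CI of the form" (π_L, 1]. The reason given is that both cohorts were sized at a one-sided 10% level. Section 12.1.2 sizes Cohort 1 at 10% and Cohort 4 at 5%.

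**Reporting in the SAP.** Section 3.8 gives 92% two-sided for Cohorts 2 and 3, 90% one-sided for Cohort 1 and 95% one-sided for Cohort 4. It also asks for a two-sided 95% interval in each cohort and says "The width of the CI will be adjusted to account for the multistage design". It does not mention that it departs from the Protocol's levels.

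**The concern.** An interval printed beside a primary endpoint should carry the same error level as the rule that decides success, or be marked as descriptive. A 98% two-sided interval puts 1% in the lower tail, whereas the Cohort 2 and 3 rule uses 4%. A 90% one-sided interval puts 10% in the tail, whereas the Cohort 4 rule uses 5%. The first is stricter than the rule and the second more lenient, so the two errors run in opposite directions.

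What is at stake is the consistency of the primary report. A cohort could be declared a success beside a protocol-specified interval that contains the null response rate, or a failure beside one that excludes it. The Protocol and SAP also prescribe different intervals for the same endpoint, which leaves room to choose between them once the data are known.

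**Working it through.** **Inputs.** Cohort 2: n = 70, null 5%, target 15%. Cohort 3: n = 52, null 10%, target 25%. Final one-sided alpha 0.04, power 90%. Cohort 4: stop at 2 or fewer of 37, success at 8 or more of 84, null 5%. Cohort 1: stop at 2 or fewer of 13, success at 13 or more of 46, null 20%. All are from Protocol 12.1.2. Assumption: exact (Clopper-Pearson) limits for Cohorts 2 and 3, since no method is named.

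**1. Reproduce the sample sizes.** N = [(z₁₋ₐ√(p₀q₀) + z₀.₉₀√(p₁q₁)) / (p₁ − p₀)]², with a = 0.04.
- Cohort 2: [(1.7507 × 0.2179 + 1.2816 × 0.3571) / 0.10]² = 70.4 (stated 70).
- Cohort 3: [(1.7507 × 0.3000 + 1.2816 × 0.4330) / 0.15]² = 51.9 (stated 52).

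The design level is therefore 4% in the lower tail. At a = 0.01, the tail of a 98% interval, the same formula rounded up gives 94 and 70.

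**2. Smallest success.** This is the smallest x with P(X ≥ x | n, p₀) ≤ 0.04.
- Cohort 2: 0.0604 at 7 and 0.0234 at 8, so 8/70.
- Cohort 3: 0.0712 at 9 and 0.0315 at 10, so 10/52.

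**3. Lower limits at and near those results.** The limit L solves P(X ≥ x | n, L) = a.

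| Result | Null | 92% two-sided (a = 0.04) | 95% (a = 0.025) | 98% (a = 0.01) |
|---|---|---|---|---|
| 8/70 | 5% | 5.56% | 5.07% | 4.28% |
| 10/52 | 10% | 10.41% | 9.63% | 8.35% |
| 11/52 | 10% | 11.90% | 11.06% | 9.68% |

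All three results are successes, and in all three the 98% interval includes the null. It first excludes the null at 9/70 (tail probability 0.0080) and 12/52 (0.0045). If the hypothesised rates are true, the chance of landing in the conflict zone is 0.8430 − 0.7412 = 10.2% for Cohort 2 and 0.8708 − 0.6768 = 19.4% for Cohort 3.

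Other methods move the boundary but keep the conflict. At each method's own smallest success, the 98% lower limits are 4.34% (7/70) and 8.37% (9/52) for Wilson, and 3.55% (9/70) and 7.98% (11/52) for Wald.

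**4. Cohort 4.** The stated design reproduces: early stopping probability 0.718, expected size 37 + 47 × (1 − 0.718) = 50.2, alpha 0.0483, power 0.901. The two-stage lower limit solves P(at least 3 of the first 37, and total ≥ s | L) = a.

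| Result | Decision | 90% one-sided | 95% one-sided |
|---|---|---|---|
| 7/84 | Failure | 5.08% | 4.28% |
| 8/84 | Success | 5.88% | 5.04% |

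The 90% level excludes 5% at a failing result. The 95% level separates failure from success at the cut-off. Without the adjustment, the 90% limit at 7/84 is 4.70%, so this conflict depends on the adjustment being applied.

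**5. Cohort 1 and the two-sided 95% intervals.** Cohort 1 reproduces (alpha 0.0965, power 0.800, expected size 29.4). Its adjusted 90% one-sided limit is 18.41% at 12/46 and 20.12% at 13/46, in agreement with the rule. The adjusted two-sided 95% lower limits are 16.4% at 13/46 and 4.38% at 8/84, both below the null. The unadjusted 95% limit for 10/52 is 9.63%, also below the null; for 8/70 it is 5.07%, above it.

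**The case against.** **The SAP already has matching levels, and no decision turns on the Protocol's intervals.** This largely stands. Both documents use the 96% one-sided limit for success in Cohorts 2 and 3 and the same responder counts in Cohorts 1 and 4. A reader might infer that the two documents require different numbers of responders for success. They do not: 9/70 and 12/52 are the counts at which a 98% interval excludes the null, and nothing makes that interval a success criterion. What remains is that the Protocol still states two wrong levels, and that Protocol 12.5 says departures from its analyses will be indicated in the SAP, which SAP 3.8 does not do.

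**The 98% level might belong to the administrative look,** since 1% per tail equals the 0.01 set aside for it. Section 12.4.5 does not limit the interval to that look, so the text does not support this reading.

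**The one-sided limits for Cohorts 1 and 4 might contradict the Simon cut-offs.** Unadjusted, 13/46 gives 19.6% and 8/84 gives 4.83% at their design levels, both below the null. But in both documents the adjustment sentence comes directly before the one-sided interval, and neither says that interval is unadjusted. This supports a request for clarification and no more.

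**Reporting a conventional 95% interval beside a decision interval is normal practice.** Agreed, provided it is labelled. For Cohorts 2 and 3 the SAP's multistage adjustment is also unclear: they now use a single-proportion test, so there is no Simon final boundary to adjust to. SAP 2.3.1 does say they changed design after moving into a second stage, so some adjustment is arguable, but the SAP would have to define it.

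**Conclusion.** The concern holds in a limited form. Protocol 12.4.5 contradicts Protocol 12.1.2 on the confidence level for Cohorts 2 and 3 (98% two-sided against 92%) and for Cohort 4 (90% one-sided against 95%). If the Protocol is followed, declared successes at 8/70, 10/52 and 11/52 carry an interval that includes the null, and a failure at 7/84 carries one that excludes it. The counts for Cohorts 2 and 3 assume exact limits, though the mismatch persists under Wilson and Wald. The Cohort 4 result assumes the two-stage adjustment.

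It would be wrong to conclude that every prescribed level is faulty or that every boundary result includes the null. Cohort 1's 90% one-sided level is correct, and Cohort 4's error is leniency. The defect concerns consistent reporting of the primary endpoint and an unrecorded change between Protocol and SAP.

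**What to change.** - **Protocol 12.4.5:** replace 98% with 92% two-sided (96% one-sided) for Cohorts 2 and 3, and give Cohort 4 a 95% one-sided interval justified by its 5% alpha. The Efficacy Analyses paragraph in the synopsis, which applies the 90% level and 10% alpha to the whole Expansion Phase, needs the same edit. If the Protocol is not amended, record the changed levels in the SAP as a deviation from it.
- **SAP 3.8:** name the interval that matches each success rule as the decision interval, and label the two-sided 95% intervals descriptive. For Cohorts 2 and 3, remove the multistage adjustment or define it, and name the interval method.
- **Clarification:** state that the one-sided limits for Cohorts 1 and 4 use the two-stage adjustment (20.1% at 13/46, 5.04% at 8/84).

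The cost is wording in the two documents. Sample sizes, cut-offs and data collection are unaffected.
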